## 4. STUDY POPULATION

## 4.1 Population

Patients with one or more jerks of psychogenic origin that significantly disable them in their daily functioning will be included in the study. Patients will be recruited in several manners. The patients with psychogenic jerks enrolled in an ongoing study focussing on the pathophysiology of jerky movement disorders will be evaluated for eligibility, (METC number 07/290) suitable patients from our outpatient clinic will be asked to participate and movement disorder specialists from other clinics will be asked to refer suitable patients.

Approximately 16 of the 54 patients participating in the BonT study will be included to take part in the fMRI study. These patients will be included at the UMC Groningen and will be included, irrespective of the randomised group that they're in. Furthermore 16 healthy control subjects will be included. Controls need to be healthy, both neurological and psychiatric, and are age- and gender- matched with the participants with psychogenic movement disorder. Controls on medication that affect the brain (like benzodiazepines/opiates/barbiturates) or with a history of substance abuse are excluded from this study.

## 4.2 Inclusion criteria

Eligible patients for the study have at least one consistent type of jerk of psychogenic origin. Two movement disorder specialists have to agree on the diagnosis based on clinical characteristics and on additional investigations if considered necessary. The diagnosis of psychogenic jerks needs to have a "definite" or "probable" level of certainty for psychogenic movement disorders. To be included, patients need to experience to be significantly impaired in daily functioning due to one specific jerk. The jerk of interest needs to be performed by a muscle or muscles amendable to injection and may be simple or complex if only treatment with BoNT is considered possible. No change in medication in the month prior to participation is allowed.

## 4.3 Exclusion criteria

- Age < 18 years or > 80 years;
- Psychogenic jerk of interest present for < 1 year;

- Previous or current treatment with BoNT;
- Pregnancy;
- Coagulation disorders;
- Insufficient knowledge of Dutch language.
- Legally incompetent adult

- No informed consent
- Patients carrying medical/metal devices or with extreme claustrophobia (only when participating in the fMRI study)

## 4.4 Sample size calculation

No prior results are available to clearly base the sample size calculation on. Hence, we chose to base our calculation on an expected difference in proportions reaching the primary endpoint between treatment with BoNT and placebo. For the expected proportions, we took the results of two prior trials studying the effect of BoNT into account. First, a trial in writer's cramp showed an effect in 32% of patients allocated to placebo and in 70% of patients allocated to BoNT on a patient rated primary endpoint. 11 Second, a cross-over trial in patients with motor tics showed no change in tics per minute in patients treated with placebo. Patients with tics and dystonia often have concurrent psychiatric disease as well. 12, 13 As the placebo effect may be large in patients with psychogenic disorders,  we expect that approximately one third of patients allocated to placebo treatment and approximately two thirds of patients allocated to BoNT may reach the primary endpoint. A two group Chi-square test with a 0,05 two-sided significance level will have 80% power to detect the difference between a control group proportion of 0,30 and a treatment group proportion of 0,70 (odds ratio of 5,4) when the sample size in each group is 24. As the side effects of therapy are mild and self-limiting and because only two injections are given in the trial period, we expect practically no withdrawals in this phase of the study. Assuming a withdrawal rate of 10 percent, we plan to include 27 patients per treatment arm, which means 54 patients in total.

This sample size calculation only concerns the trial part of this study, no power analysis was done for the follow-up study.

Regarding the fMRI study approximately 16 of the 54 patients participating in the BonT study will be included to take part in the fMRI study. Based on a study by Thirion et al., a minimum of 16 subjects is required for fMRI studies (see also amendment 2).

## 5. TREATMENT OF SUBJECTS

## 5.1 Investigational product/treatment

Patients will be randomized to treatment with:

- 2 times injections with botulinum neurotoxin injections intramuscular with a 3 month interval or
- 2 times injections of placebo intramuscular with a 3 month interval.

Placebo will consist of 0.9% sterile saline. This is a frequently used placebo in studies on botulinum toxin. 

After the trial period, all patients will receive 4 injections of BoNT also with 3 month intervals.

## 5.2 Use of co-intervention

During the study, the patients continue their previously prescribed therapy. Patients will not be allowed to use medication (benzodiazepines, opiates, barbiturates) in such dosages that it might affect the performance on neuropsychological tests. No change in medication in the month prior to participation is allowed. During the study, changes in concurrent medication will be discouraged but will be registered if they do occur.

## 5.3 Escape medication

If patients experience adverse effects like pain or flu like symptoms, usage of NSAID or paracetamol is allowed, no interactions with BoNT have been described.

## 6. INVESTIGATIONAL MEDICINAL PRODUCT

## 6.1 Name and description of investigational medicinal product(s)

Dysport®, botulinum neurotoxin type A, will be compared to placebo (sterile saline).

# 6.2 Summary of findings from non-clinical studies

There is no pre-clinical information that has not been included in sections of the Summary of Product Characteristics of Dysport® (pg.7-9).

# 6.3 Summary of findings from clinical studies

In the clinical trial programme, approximately 28% of the patients treated with Dysport® experienced an adverse event. The following adverse reactions were seen in patients treated across a variety of indications including blepharospasm, hemifacial spasm, torticollis and spasticity associated with either cerebral palsy or stroke:

• Rare: neuralgic amyotrophy

• Uncommon: itching

Rare: skin rashes

Common side effects are: generalised weakness, fatigue, flu-like syndrome, pain / bruising at injection site.

No side effects have been found in clinical studies concerning placebo (see SPC sterile saline).

## 6.4 Summary of known and potential risks and benefits

Dysport® is contraindicated in individuals with known hypersensitivity to any components of Dysport®, careful consideration should be given before the injection of patients who have experienced a previous allergic reaction to a product containing botulinum toxin type A Side effects related to spread of toxin distant from the site of administration have been reported, which in some cases was associated with dysphagia, pneumonia and /or significant debility.. The occurrence of these side effects though are rare. Common side effects are: generalised weakness, fatigue, flu-like syndrome, pain / bruising at injection site. These side-effects are reversible and may be expected to resolve within two to four weeks.

No potential risk factors have been described concerning placebo(see SPC placebo).

# 6.5 Description and justification of route of administration and dosage

Dysport® is only available as powder for injection, after dissolving it is a colourless fluid indistinguishable from sterile saline. Both Dysport® and sterile saline will be administrated by intramuscular injection. The muscles that will be injected will be determined by a neurophysiologist experienced in treatment with BoNT according to the pattern of movements visible and according to the involved muscles measured with EMG. If more jerks are eligible, one jerk of interest will be selected by the patient prior to the first administration. During the entire study, therapy will be aimed at this particular jerk. The number of muscles injected may differ per patient.

# 6.6 Dosages, dosage modifications and method of administration

For individual patients, the dose of botulinum toxin to be injected will be determined based on the number and type of muscles that are involved in performing the jerk. The muscles that will be injected will be determined by a neurophysiologist experienced in treatment with BoNT according to the pattern of movements visible and according to the involved muscles measured with EMG. Hereafter the local farmacy will prepare the determined dosage of BoNT or sterile saline 0.9%. In this manner the neurophysiologist will remain blinded. The dosage of BoNT depends on the volume of the muscle(s) it is injected in and guidelines for starting dosages and for adjustments after the first injection for individual muscles exist. These guidelines will be used for the treatment of psychogenic jerks in this study.  Because the dosage of BoNT depends on the muscles to be injected, individual patients will receive different dosages. The dilution volume of Dysport will be 500 units in 2.5 cc of 0.9% saline. If there is no effect of the treatment the the first time, the dosage will be doubled during second treatment. The maximum dosage per treatment session is 400 Dysport units. BoNT is an accepted and widely-used therapy for dystonia and as such a great deal of experience is available.

# 6.7 Preparation and labelling of Investigational Medicinal Product

Dysport® and placebo will be prepared, blinded and labelled by Ipsen BV, a pharmaceutical company that works according to GMP guidelines. The medication will be transported to the pharmacy of the Academic Medical Center, where it will be checked and approved. To remain double blind the local pharmacy of the Academic Medical Center will prepare botulinum toxin or placebo, according to the dosage determined by the neurophysiologist, for the individual patients according to a randomization list. This is necessary because BoNT is may only be stored for up to 8 hours following reconstitution. The syringes will not contain

information on the allocated treatment. This way the person that performs the injection, the patients and other persons involved in the trial, will remain blind for the supplied therapy.

# 6.8 Drug accountability

Dysport and placebo will be requested from its direct supplier, Ipsen BV. To remain double blind the local pharmacy of the Academic Medical Center will prepare placebo or botulinum toxin for the individual patients according to a randomization list. The syringes will not contain information on the allocated treatment.

If any study medication remains at the end of the study, the medication will be returned to the AMC pharmacy, where it will be destroyed.

## 7. METHODS

## 7.1 Study parameters/endpoints

## 7.1.1 Main study parameter/endpoint

The primary study endpoint for the trial will be improvement of motor characteristics of the jerk of interest assessed with the Clinical Global Impression - Improvement scale (CGI-I). On this 7 point scale can be assessed how much the patients illness has improved or worsened relative to the baseline state. It can be rated as: 1, very much improved; 2, much improved; 3, minimally improved; 4, no change; 5, minimally worse; 6, much worse; or 7, very much worse. We will consider a score 1, 2 or 3 determined by an experienced researcher as reaching the primary outcome. The primary outcome will be determined 4 weeks after the second injection (t=16 weeks) as the optimal effect of BoNT is between 4 and 8 weeks after the injection. One researcher who is blind to allocated treatment will assess the CGI-I in all patients based on videos of the patient.

The CGI-I scale is one of the few rating scales that is considered suitable for psychogenic movement disorders at this moment.

# 7.1.2 Secondary study parameters/endpoints

- 1. Clinical Global Impressions-Severity of Illness Scale (CGI-S) for motor severity of illness, including other jerks, rated by the investigator;
- 2. Severity and improvement of the jerk of interest according to the patient. The CGI-I will be used for the improvement of the jerk of interest, including other jerks, rated by the patient; The severity will be measured using the CGI-S and the Visual Analogue Scale(VAS). This is a self assessment scale drawn by the patient on a 10 cm line, on which 0 indicates no disease burden and 10 indicates the worst possible disease burden: 
- 3. Severity of general dyskinesia and myoclonus according to a movement disorder specialist using two scales; the unified myoclonus rating scale (UMRS) , which measures the nature, distribution and severity of dyskinesia and a recently developed PMD scale, which quantifies the impact of the movements and is a valid measure of severity. It is used to assess PMDs and test the efficacy of intervention strategies;
- 4. Frequency of the jerk of interest during the psychiatric interview;
- 5. The patients answer to the following questions: considering all advantages and disadvantages of this treatment, is the improvement such that you want to continue this treatment or not? 

- 6. AMC Linear Disability Score (ALDS), a generic instrument which includes ADL and instrumental activities of daily living;
- 7. Short-Form-36(SF-36), a generic Quality of Life scale, suitable for measuring disease burden and health benefits produced by a wide range of different treatments;
- 8. Psychiatric evaluations including the Mini-International-Neuropsychiatric Interview Plus (MINI-Plus) and several questionnaires concerning symptoms of depression, anxiety and obsessive-compulsive disorders. The Yale Tic severity scale and the Premonitory Urge for Tics Scale (PUTS), will be used for assessment of tics and evaluation of premonitory urge in the jerk of interest;
- 9. Evaluation of adverse effects via interview and neurological examination;
- MRC scale for testing muscle strength and sensibility;
- 11. Changes in brain function assessed with fMRI.

Outcome measures 2, 5, 6, and 7 will be completed by the patients. Measure 1, 3 and 4 will be based on the video recordings and will be completed by the same independent investigator who is blind to treatment and is not involved in the injections based on the video of the patients. The psychiatric evaluations will be performed by a neuropsychologist specifically trained to perform the MINI-plus psychiatric interview.

A time schedule of the study is presented at page 14. For the trials secondary outcome measures, similar to the primary outcome measure, the difference in scores between baseline and after 16 weeks (4 weeks after the second injection) will be used. To evaluate the long term effect of treatment with BoNT the different outcome measures assessed 16 months after the start of the study (approximately 1 year after the end of the trial) will be compared with baseline (t=0) and with the assessments at the end of the trial period (t=16 weeks)

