## **Secondary Objectives:**

To asses, in patients with psychogenic jerks, the effect of treatment with BoNT on:

- · the severity of the invalidating jerk of interest scored by a movement disorder specialist;
- improvement of motor characteristics and severity of the invalidating jerk of interest scored by the patient;
- the nature, distribution and severity of overall dyskinesia, scored by a movement disorder specialist;
- the frequency of the invalidating jerk of interest;
- whether patients consider treatment with BoNT effective and whether they judge that the benefits of treatment outweigh the side-effects;
- disability;
- · quality of life;
- co-existent psychiatric disorders;
- · the occurrence of adverse reactions;
- muscle weakness;
- · difference in brain function measured by fMRI

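### The investigator CGI-S and the patient CGI-I take in other jerks, although the secondary objectives they serve, and the therapy, concern one selected jerk of interest

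*Protocol*

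**What the plan says.** Protocol section 2 (Secondary Objectives) lists first "the severity of the invalidating jerk of interest scored by a movement disorder specialist" and second "improvement of motor characteristics and severity of the invalidating jerk of interest scored by the patient". Both are tied to one jerk. The follow-up objectives repeat the same targets. Overall dyskinesia is a separate objective.

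Section 6.5 explains how that jerk is chosen and used: "If more jerks are eligible, one jerk of interest will be selected by the patient prior to the first administration", and then "During the entire study, therapy will be aimed at this particular jerk". Section 3 admits patients with one jerk or with several.

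Section 7.1.2 sets the endpoints:

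- Item 1, the investigator CGI-S, is rated "for motor severity of illness, including other jerks, rated by the investigator".
- Item 2 opens with "Severity and improvement of the jerk of interest according to the patient" and continues: "The CGI-I will be used for the improvement of the jerk of interest, including other jerks, rated by the patient". Patient-rated severity (CGI-S and a VAS anchored to disease burden) follows, with no statement about other jerks.
- Item 3 covers general dyskinesia and myoclonus with the UMRS and the PMD scale. Section 7.1.2 has these scored from video by the blinded investigator.

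The primary endpoint in section 7.1.1 is the CGI-I for motor characteristics of the jerk of interest.

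**The concern.** An endpoint should measure what its objective asks. Here the objective names one jerk and two of the ratings meant to answer it cover all jerks. Item 2 also contradicts itself: a patient whose selected jerk is better while another is unchanged has no defined answer to give.

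Two things are at stake. First, the specialist's view of the severity of the treated jerk may never be recorded. Second, the natural comparison between the blinded rater's CGI-I and the patient's CGI-I would set different targets against each other on the same 7-point scale, so disagreement could not be read as a difference in perception. The same ratings are used at 16 weeks and at 16 months, so both parts of the project are touched.

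**Working it through.** **The plan's own figure.** Section 4.4 sizes the trial on the primary endpoint only and gives no figure for these two ratings. It reproduces: n per arm = [1.96 × √(2 × 0.5 × 0.5) + 0.8416 × √(0.3 × 0.7 + 0.7 × 0.3)]² / 0.4² = (1.386 + 0.545)² / 0.16 = 23.3, rounded up to 24. Then 24 / 0.9 = 26.7, rounded up to 27, and 2 × 27 = 54. Nothing in this point changes it.

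**Scope of each measure, side by side.**

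| Measure (protocol section) | Target in the objective | Target in the endpoint text |
|---|---|---|
| Primary CGI-I, blinded rater (7.1.1) | jerk of interest | jerk of interest |
| Investigator CGI-S (7.1.2, item 1) | jerk of interest | all jerks |
| Patient CGI-I (7.1.2, item 2) | jerk of interest | heading: jerk of interest; text: other jerks added |
| Patient CGI-S and VAS (7.1.2, item 2) | jerk of interest | heading: jerk of interest; otherwise unstated |
| UMRS and PMD scale (item 3) | overall dyskinesia | overall |
| Jerk count (item 4) | frequency of jerk of interest | jerk of interest |

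**Does another endpoint supply the missing one?** The first secondary objective needs a specialist's severity rating of the jerk of interest. The primary CGI-I gives improvement, item 3 gives overall movement, and item 4 gives frequency. The tic scales in item 8 sit among psychiatric evaluations assigned to a neuropsychologist. None of these fills the gap. The interview and visit lists in section 7.3 name CGI-S and CGI-I without stating a scope, so they do not settle it either.

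**Can the effect on the ratings be sized?** Only under assumptions the protocol does not supply. Treat the mixed rating as s × (treated jerk) + (1 − s) × (other jerks), with equal SDs and correlation ρ, and let other jerks respond with k times the effect on the treated jerk. The effect becomes s + (1 − s)k of its single-jerk size, and the variance is multiplied by s² + (1 − s)² + 2ρs(1 − s). The number needed for the same power is multiplied by

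M = [s² + (1 − s)² + 2ρs(1 − s)] / [s + (1 − s)k]².

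At s = 0.5 the numerator runs from 0.50 (ρ = 0) to 1.00 (ρ = 1). At s = 0.7 it runs from 0.58 to 1.00.

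| k (assumed) | M at s = 0.7, ρ from 0 to 1 | M at s = 0.5, ρ from 0 to 1 |
|---|---|---|
| 0 (others unchanged) | 0.58/0.49 = 1.2 to 1/0.49 = 2.0 | 0.50/0.25 = 2.0 to 1/0.25 = 4.0 |
| 0.5 | 0.58/0.7225 = 0.80 to 1/0.7225 = 1.4 | 0.50/0.5625 = 0.89 to 1/0.5625 = 1.8 |
| 1 (others respond equally) | 0.58 to 1.0 | 0.50 to 1.0 |

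If other movements worsen under treatment (k below 0), M exceeds the first row. A patient with a single jerk has s = 1 and M = 1. The results lie on both sides of 1, so the arithmetic fixes neither the direction nor the size.

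**The case against.** The strongest reply is that this is loose wording in two secondary measures with no demonstrated loss. A reader might infer that untreated jerks necessarily dilute the effect, so that two to four times as many patients would be needed. The protocol does not support that:

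- Section 1 hypothesises that the toxin may restore changes in the central nervous system, in which case other jerks could improve too. Section 10.4 warns that other somatic symptoms may appear, which would pull an all-jerk rating the other way.
- Section 6.5 says therapy is aimed at one jerk. It does not say that muscles shared with other jerks are spared.
- The share of patients with more than one jerk is nowhere given. The multipliers of 2.0 and 4.0 for s = 0.7 and s = 0.5 hold only if other jerks do not change and the mixed rating keeps the full SD. A CGI is one global judgement, not a weighted mean.

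All of this stands and removes any claim about size.

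It can also be said that the Summary speaks of jerks in the plural for both the primary outcome and the specialist's severity rating, and that section 7.1.1 describes the CGI-I scale as referring to the patient's illness. The objective could therefore be the line to amend. That would remove the contradiction, but would leave the treated jerk without a specialist severity rating. It would also make the first secondary objective overlap with the one on overall dyskinesia. Sections 2 and 7.1.1 both name the jerk of interest, so the wider rating is the odd one out.

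**Conclusion.** The mismatch between objective and endpoint is explicit, and nothing else in the protocol resolves it. It affects two secondary ratings, the investigator CGI-S and the patient CGI-I, and should be corrected. The primary endpoint and the sample size are untouched.

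The conclusion rests on the text alone: whichever way other jerks move, a rating that includes them answers a different question from the stated objective. In patients with other jerks the result may be diluted or shifted, by an amount the protocol does not allow anyone to compute. In patients with one jerk the two scopes coincide.

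A reader might also infer that the second secondary objective has lost its endpoints altogether. That goes too far. Patient-rated severity stands under a heading that names the jerk of interest and is not said to include other jerks. Its scope is merely unstated, and the VAS anchor is broad.

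**What to change.** In section 7.1.2, items 1 and 2, have the investigator CGI-S and the patient CGI-I rated on the jerk of interest selected before the first administration, matching the target of the primary CGI-I. State the same scope for the patient CGI-S and the VAS. Carry the wording onto the rating form for both the 16-week and the 16-month assessments.

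If an all-jerk rating is wanted, keep it as a separate, labelled item. The UMRS and the PMD scale do not make a patient version redundant, because they are scored by the investigator from video.

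The cost is a reworded rating form and at most one extra question. The number of patients, the visits and the treatment do not change.
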